C.3.b. Enrollment Session. Upon obtaining consent /assent, an enrollment session will be scheduled. At this session students' height and weight will be measured and they will complete an online enrollment survey addressing preferences, baseline characteristics, current habits, values, ethnic identity , their level of interest in making dietary changes and any changes they might wish to make. They will download the app and receive instruction in its use, including photo submission and rating foods on a Likert scale of very healthy to very unhealthy. They will be informed that they will be randomly assigned to use one of three versions of the app by the technology team who will apply to appropriate functionality to their app.

Ame00110293

Due to recruitment and enrollment efforts being conducted virtually because of the COVID-19 pandemic, participants will be guided as they take their own height and weight measurements. Since this will be done remotely, we will send any participants who require a scale, a tape measure, a square, and/or pencils, the necessary materials, which they will be able to keep.

Randomization – The technology team will randomly assign participants as they enroll to either the intervention or one of the control groups. They will then adjust the functionality of the app for the participants accordingly, and will send a message to their phone indicating their group assignment, along with instructions for their group. Thus, the research assistant who collects data will be blinded regarding group assignment.

C.3.c. Four Week Intervention

Week 1 – Student Registration of Eating Venues. Students will be asked to identify, using ActiPal, when they are in an eating venue (cafeteria, restaurant, or convenience store). The venue data (time and location) are registered

in PiLR. They will be encouraged to submit a photo of their food choices and annotate it with a rating on the very healthy to very unhealthy scale.²⁸ By the end of week 1 the system will have collected data about the most frequent eating locations, when they typically eat there, and what food they choose.

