Intervention Group 1 – Participants will be asked to keep the app running on their phone. They will receive a ping when the app identifies that they are in a fast food restaurant followed by a point of purchase prompt, tailored to their preferences and the options available at that location. If they are in a venue without a menu, general healthy suggestions will be provided (such as “consider choosing smaller portions” or “does this venue sell fruit?”). If the app does not ping when they enter a restaurant, they will be asked to register that location by tapping the ‘register location’ button on the app and entering the restaurant name. For detection errors, the appropriate stored venue criteria (location, geo-fence, time of day or dwell time) may be adjusted to improve detection. Users will also be asked to take a picture of any items they buy and to annotate it with information that would help to determine the nutrients in the food. Annotations may be audio, text, or made from a selection of descriptive buttons (e.g., to indicate small, medium or large sizes).

Control Group 2 – Participants in Control Group 2 will receive similar instructions to those given to group 1, but without receiving point of purchase prompts.

Control Group 3 – The Location Only Control Group 3 will only get information about location detection, and asked to register FFR if the app does not indicate with a ping that they have entered one. Their instructions will not discuss photo documentation of food or prompts as these features will not be active on their app.

During the study period, the participants will be contacted once per month by a research team member. Monthly calls will be added to help gather feedback from participants about the app. Study participants will be contacted by phone on three separate occasions, at times when the participants are not in school (e.g. after 4pm on weekdays or a weekend). If, for any reason, a research team member is unable to reach a study participant after three attempts, we will connect with the parent and/or research liaison (e.g. a staff member at the school or community organization we are working with) for assistance.

C.3.d Post Intervention Assessment

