Based on students' responses when using the system we will determine 1) the percentage of the time that the system accurately identified presence in an eating venue and correctly identified the registered venue (cafeteria vs. convenience store), and 2) the percentage of time that an appropriate and relevant message was delivered.

For this amendment, calories purchased will be assessed using submitted annotated photos, and nutrition data from FFR menus (e.g., if the participant submits a picture of McDonald's fries and indicates it is a small order, then from the McDonalds menu, we will determine that the calories purchased were 240 kcals). Frequency of visits will be obtained directly from the app. We will use population averaged generalized estimating equation regressions (GEE) to compare trajectories of calories purchased and number of visits between groups. The GEE approach allows us to account for the correlation in repeated observations collected from each subject over time. For calories purchased, we will perform GEE linear regression modeling as a function of time, treatment group (intervention vs. control group 2) and the interaction of time by treatment group ($Y = \beta_0 + \beta_1 Time + \beta_2 Treatment + \beta_3 Time * Treatment + \epsilon$). Similarly, for the number of visits, we will fit a GEE Poisson regression model as a function of time, treatment group (intervention vs. control group 2 vs control group 3) and the interaction of time by treatment group. Residual diagnostics will be performed to examine departures from model assumptions. If necessary, we will use transformed outcome variables and refit the models.

Secondary Outcome 1 – Acceptability of the intervention and the messages

From the post-pilot interviews we will identify students' perceptions of the intervention overall and of the messages specifically. We will explore opinions of school personnel on impacts of using the LiTAH at school. Data from post-pilot interviews plus the advisory board input, will inform revisions of the app and planning for a larger trial.

For this amendment, we will use the models discussed above to examine associations between calories purchased /number of visits including as covariates participant characteristics such as extent of app use, initial BMI, and ethnic identity (as an ordinal measure assessed via the Multiethnic Identity Scale) as a secondary outcome.

Secondary Outcome 2 – Exploration of food choices

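### Recorded calories depend partly on the participant's own size annotation, which no stated check verifies and which in Group 1 alone follows a prompt, so excess size under-reporting in Group 1 would lower its calories with no change in purchases

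*Combined protocol and SAP*

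**What the plan says.** Under the amendment text in section C.3.e (Analyses), "calories purchased will be assessed using submitted annotated photos, and nutrition data from FFR menus". The only worked example is a case where, "if the participant submits a picture of McDonald's fries and indicates it is a small order", the menu is consulted and "we will determine that the calories purchased were 240 kcals". Section C.3.c (Intervention Group 1) describes how the size is entered: annotations may be spoken, typed, or "made from a selection of descriptive buttons (e.g., to indicate small, medium or large sizes").

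The same section gives the order of events. In Group 1 a ping is "followed by a point of purchase prompt, tailored to their preferences and the options available at that location". Then: "Users will also be asked to take a picture of any items they buy and to annotate it". Control Group 2 gets similar instructions but no prompts. One sample prompt, offered for venues that have no menu, is "consider choosing smaller portions".

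Under Randomization in section C.3.b, the technology team "will send a message to their phone indicating their group assignment, along with instructions for their group". Blinding is claimed only for the research assistant who collects data.

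The calorie model in C.3.e is a linear GEE with time, treatment (Group 1 against Group 2) and their interaction. The plan speaks of comparing trajectories but does not name the coefficient to be tested. It describes no receipt, no coding of size from the image by someone blinded to group, no rule for a conflict between photo and annotation, and no validation subsample.

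**The concern.** The size entry helps select the menu value, so it feeds directly into the outcome. It is self-reported by an unblinded adolescent who, in one arm only, has just been encouraged to choose well. Blinding the research assistant does not protect an entry that the participant makes. If the encouragement shifts what is reported rather than what is bought, the shift appears as a difference in calories. GEE handles within-person correlation, and residual diagnostics check model fit; neither would reveal it.

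At stake is the amended Aim 3 question of whether app use goes with fewer calories purchased, and the planned R01 that the pilot is meant to inform. Section C.3.c says weeks 1 to 3 are not repeated, and no calorie data collected before prompting are described. An immediate real effect and an immediate reporting shift therefore cannot be told apart.

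**Working it through.** **Inputs from the documents.** Calories come from photo, annotation and menu (C.3.e). The example value is 240 kcal for small fries; no value is given for other sizes. The contrast is Group 1 against Group 2 (C.3.e). Follow-up is 1 month (C.3.c). The recruitment figure is 150, with wording that can be read as a total or as a number per city (C.3.a). The plan states no bias, SD, effect size, alpha or power, so there is no figure of its own to reproduce.

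**Assumed inputs.** *k* = size-dependent items per order; *d* = kcal between the true and the reported size; *m*1 and *m*2 = share of such items reported too small in Groups 1 and 2.

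**Step 1: bias in the group difference.**

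Recorded difference = true difference - *k* x *d* x (*m*1 - *m*2).

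Only the excess, *m* = *m*1 - *m*2, matters; under-reporting at the same rate in both groups cancels.

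- Per order, *k* = 2 and *d* = 100: 2 x 100 x 0.10 = 20 kcal; 2 x 100 x 0.20 = 40 kcal.
- Per item (*k* = 1), for *m* from 5% to 30%: *d* = 80 gives 4 to 24 kcal; *d* = 120 gives 6 to 36 kcal; *d* = 200 gives 10 to 60 kcal.

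**Step 2: where the bias lands in the planned model.** The model is Y = β0 + β1 Time + β2 Treatment + β3 Time x Treatment. Take zero true effect, weeks coded 0 to 3, *d* = 120, one item.

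| Excess misreporting, weeks 0-3 | Shift in Group 1 (kcal) | β2 | β3 (per week) | Mean difference |
|---|---|---|---|---|
| constant 20% | -24, -24, -24, -24 | -24 | 0 | -24 |
| growing 0, 10, 20, 30% | 0, -12, -24, -36 | 0 | -12 | -18 |
| fading 30, 20, 10, 0% | -36, -24, -12, 0 | -36 | +12 | -18 |

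A constant excess leaves β3 at zero. A growing excess makes β3 favour the intervention; a fading excess makes it go the other way.

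**Step 3: effect on a nominal 5% test.** GEE simulation with exchangeable correlation, zero true effect, *d* = 120, 12 items per person, assumed SDs of 80 kcal between and 150 kcal within persons, 200 runs per setting. The 50 and 150 per arm correspond to 150 or 450 in total split equally over three groups; the plan does not state the allocation ratio.

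| Per arm | Excess | Rejects β2 | Rejects β3 | Rejects mean difference |
|---|---|---|---|---|
| 50 | none | 2% | 4.5% | 3.5% |
| 50 | constant 20% | 19.5% | 4.5% | 24.5% |
| 50 | growing 0-30% | 8.5% | 42% | 18% |
| 150 | none | 7% | 8.5% | 4.5% |
| 150 | constant 20% | 51% | 6% | 63.5% |
| 150 | growing 0-30% | 4.5% | 71.5% | 38% |

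With 200 runs, the simulation standard error is about 1.5 points near 5% (√(0.05 x 0.95/200)) and about 3.5 points near 42% (√(0.42 x 0.58/200)). The table shows which term is exposed; it does not predict this trial.

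**The case against.** A reader might infer more than the documents support, and the counter-arguments deserve weight.

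- **That the size button alone fixes the calories.** The fries case is an example, the photo is part of the assessment, and C.3.c presents the annotation as an aid to working out nutrients. A coder may well notice a wrong size. This stands as a limit on the wording. But no rule requires the check or says which source prevails.
- **That Group 1 is told to buy smaller and then asked the size.** The portion-size wording is an example for venues without a menu, where the menu lookup may not apply. Elsewhere prompts are tailored to preferences and available options; section C.2 gives the example of suggesting a parfait, which concerns the item, and the item can be seen in the photo. This stands: at menu venues the pressure is toward looking healthy in general, not toward size in particular. The text also gives only the order of prompt and annotation, not the interval.
- **That the bias always favours the intervention.** Step 2 shows otherwise for β3. It remains true of β2 under a constant excess, and the plan does not say which term decides.
- **That misreporting will occur.** Nothing in the documents shows an excess in Group 1. Group 2 also photographs and annotates, in a study about healthy choices, and may shade sizes too.

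It is also fair to say that this is a one-month pilot and that its visit outcome comes from the app. Both lower the urgency, but neither supplies the missing check.

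**Conclusion.** The point holds in conditional form. Calories purchased rest on a photo plus a self-reported size, with no stated verification. The self-report follows a prompt given to only one side of an unblinded comparison. Any excess under-reporting in Group 1 over Group 2 would lower its recorded calories without any change in purchases: through β2 if the excess is constant, and through β3 only if it changes over time, in either direction.

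The size cannot be derived from the documents. The 20-40 kcal per order is illustrative and rests on three assumptions: two sizeable items, 100 kcal per size step and 10-20% excess misreporting. The documents do not support a claim that a calorie reduction in this pilot would be an artefact. This is a worthwhile, inexpensive improvement to how one outcome is measured, not a defect that undermines the pilot.

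**What to change.** 1. Instruct Groups 1 and 2 alike to include the size label, packaging or receipt in the photo when available.
2. Have the photo coders, blinded to group, record size from the image, label or receipt before they see the annotation. Use the annotation only when size cannot be read. Where sources disagree, the image or receipt takes precedence.
3. Report by group the share of items sized by annotation alone and the rate of disagreement between image and annotation.
4. Keep all items in the main calorie comparison. Add a sensitivity analysis over a range of assumed excess misreporting for annotation-only items, with both constant and time-varying patterns.
5. Label any comparison limited to verified items as descriptive: that subset is selected by behaviour after randomisation, which the prompts may influence.

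**Cost.** One line in the app instructions, an added size-source field and a coding order on the photo form, and a short addition to C.3.e. Participants make slightly more effort, and somewhat fewer photos may be submitted. Bias remains possible where no label or receipt is shown, since a participant who shades size can also leave it out; items 3 and 4 make that remainder visible but do not remove it.

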Semi-Structured Interviews. At the completion of the 6-month trial (or sooner if they appear to have dropped out), adolescents will be interviewed to obtain detailed feedback about PiLR, the subject interface, methods of prompting, EMA surveys, entering data, submitting photos and rating foods. Location data will be used to inform the questions in the interview. For example, participants who, based on the GPS, have not visited FFR will be asked to share reasons for this change. Those who, based on the GPS, continue to visit FFR, will be asked about the choices made, and what if anything would be most helpful to them when they are making the choice regarding what to

purchase. They will also be asked about the user interface, cultural tailoring, and the SNAP component. Interviews will be transcribed and coded by 2 researchers separately.

For the semi-structured interviews at the end of the study period, study participants will be contacted by phone on three separate occasions, at times when the participants are not in school (e.g. after 4pm on weekdays or a weekend). If, for any reason, a research team member is unable to reach a study participant after three attempts, we will connect with the parent and/or research liaison (e.g. a staff member at the school or community organization we are working with) for assistance.

We have shortened our study period time frame from 6 months to 1 month due to the COVID-19 pandemic.

Quantitative Survey. *Acceptability Measure:* A questionnaire will assess acceptability of the format (What was their experience, did they like it?; How would you rate the overall experience?), and feasibility (How easy was it to use the hardware and respond to prompts?). Acceptability and feasibility mean scores of 3.5 or greater, rated on a scale of 1 (poor) to 5 (excellent), are deemed acceptable.

Assessment of Usage. *Electronic Usage Measures:* During the pilot, the PiLR will automatically record (1) the time students spent using the system, (2) the frequency of triggering events, (3) compliance with prompts, (4) and whether subjects felt the system was responsive. It will automatically record number of visits to the FFR. It will also collect usage data in regard to things like frequency of submitting pictures and whether they include annotations.

C.3.e. Analyses

Primary Outcome – Feasibility of the technological components

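### App-counted fast food visits are modelled with no offset for monitored time and no app-off rule: if the between-arm ratio of capture changes over the month, the planned trajectory comparison is biased, by an unknown amount and in an unknown direction

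*Combined protocol and SAP*

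**What the plan says.** In the combined protocol and SAP, C.3.e (Analyses) states "Frequency of visits will be obtained directly from the app", and C.3.d (Assessment of Usage) says of the server system "It will automatically record number of visits to the FFR". No other source for this outcome is named.

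The purpose of the GEE models is to "compare trajectories of calories purchased and number of visits between groups". For visits, "we will fit a GEE Poisson regression model as a function of time, treatment group (intervention vs. control group 2 vs control group 3") together with the time-by-group interaction. No offset, definition of monitored time or length of time period is given.

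Other relevant places:

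- C.3.c requests that participants leave the app on. The three arms run different versions: prompts and photos in Group 1, photos only in Group 2, location detection only in Group 3. There is a manual back-up: "If the app does not ping when they enter a restaurant, they will be asked to register that location". Stored venue criteria may be adjusted during follow-up.
- C.3.d (Semi-Structured Interviews): "participants who, based on the GPS, have not visited FFR will be asked to share reasons for this change". An absence of recorded visits is thus taken as behaviour to be explained.
- C.3.d (Assessment of Usage): "the PiLR will automatically record (1) the time students spent using the system". This is not said to be the time in which a visit could have been detected.
- C.3.e (Secondary Outcome 1): the models are rerun "including as covariates participant characteristics such as extent of app use, initial BMI, and ethnic identity".

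**The concern.** An app that is switched off, removed or without location data records nothing, and nothing in the plan distinguishes that from a participant who stayed away from FFR. Followed as written, the model reads unmonitored time as zero visits.

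Because the arms use different app versions, the time for which the app is left on may differ between them, and the difference may grow as interest fades. Fewer FFR visits is one of the amended aims (Specific Aims, Aim 3), and the pilot is meant to inform a larger proposal. A difference in capture could be carried forward as an effect of the prompts, or could hide one.

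**Working it through.** The plan gives no visit rate by arm, capture rate, power or effect size, so there is no figure to reproduce. The check is algebra followed by an illustration.

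**Algebra.** Let c_g(t) be the share of true visits recorded in arm g at time t. Under a log link, log E[recorded] = log(true rate) + log c_g(t). With no offset, log c_g(t) is absorbed by the coefficients:

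- c_1/c_2 constant: all of it goes into the group term; the interaction is untouched.
- c_1/c_2 changing: part goes into time by group.
- c_1 = c_2 throughout, even if both decline: group ratio 1.000 and interaction ratio 1.000.

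The constant quantity must be the ratio. With a constant absolute gap of 0.15 (0.70 to 0.50 against 0.85 to 0.65), the ratio moves from 0.824 to 0.769, which is (0.769/0.824)^(1/3) = 0.978 per week.

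**Inputs.** From the documents: 3 visits per week (the eligibility floor in C.3.a), a one-month study, three arms. C.3.a can be read as 150 or 450 participants in total, so with equal allocation (assumed) 50 or 150 per arm. Everything else is assumed: uptime u, four weekly periods, and r, the share of app-off visits registered by hand. Recorded share: c = u + (1 − u)r. No true effect.

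**Constant ratio, u = 0.70 against 0.85**

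- r = 0: 0.70/0.85 = 0.82
- r = 0.25: 0.775/0.8875 = 0.87
- r = 0.5: 0.850/0.925 = 0.92
- r = 0.75: 0.925/0.9625 = 0.96

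This affects the group term only; simulated interaction rejections stay at 5% to 7%.

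**Changing ratio, Group 1 from 0.85 to 0.65 by week 4, Groups 2 and 3 flat at 0.85**

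- r = 0: week-4 ratio 0.65/0.85 = 0.765; per week 0.765^(1/3) ≈ 0.91
- r = 0.5: week-4 ratio 0.825/0.925 = 0.892; per week 0.892^(1/3) ≈ 0.96

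If Group 2 declines instead, these become about 1.09 and 1.04.

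**False positives** for the 2-df time-by-group test at the 5% level. Settings: 2,000 replicates, Poisson GEE, independence working correlation, robust standard errors, gamma frailty variance 0.25, uptime varying between persons.

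| Group 1 uptime falls to | r | 50 per arm | 150 per arm |
|---|---|---|---|
| 0.75 | 0 | 11% | 23% |
| 0.75 | 0.5 | 8% | 9% |
| 0.65 | 0 | 32% | 73% |
| 0.65 | 0.25 | 19% | 46% |
| 0.65 | 0.5 | 12% | 21% |
| 0.65 | 0.75 | 7% | 10% |
| 0.55 | 0 | 59% | 98% |
| 0.55 | 0.5 | 18% | 43% |

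Counting visits within uptime with offset log(uptime) brought the rates to 4% to 7%. Weeks with no active day were left out of every model (about 0.24% of Group 1 weeks in the fall to 0.65), so the separate effect of scoring such weeks as zero is not in these figures.

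**Does the secondary covariate help?** Adding each person's exact mean uptime left the interaction test unchanged: 35%/77% at r = 0 and 11%/23% at r = 0.5 (50/150 per arm, fall to 0.65, 1,000 replicates), with or without it.

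**Which visits to count.** Take equal uptime 0.85, automatic detection 0.8, and hand registration of missed visits 0.25 against 0.5:

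- As planned: (0.85×0.85 + 0.15×0.25)/(0.85×0.90 + 0.15×0.5) = 0.76/0.84 = 0.90
- Automatic plus hand-registered within uptime, with offset: 0.85/0.90 = 0.94
- Automatic only, with offset: 0.8/0.8 = 1.00

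**The case against.** The bias is conditional. No document says that uptime differs by arm. All arms have location detection and are asked to register missed venues, and Groups 1 and 2 differ only by the prompts. If capture declines equally, the comparison is unharmed. This stands, and it is why size and direction must be left open. A reader might infer that the visit result will be biased, or biased towards the intervention; the documents support neither. A reader might also infer that any constant gap spares the trajectory comparison; that is true only of a constant ratio.

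Safeguards exist. B.1 describes automatic restart, C.3.c the register button, C.3.e a detection-accuracy outcome and a covariate for extent of app use. They reduce or describe the loss, but none corrects the main model. The accuracy outcome rests on responses given while using the system, so it does not cover app-off time. The covariate is undefined, secondary and measured after randomisation. Interviews may reveal app-off cases but do not feed the model. No section says whether a hand registration counts as a visit, so every figure with r above 0 rests on the reading that it does.

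The offset is not always better, and this also stands. It assumes similar visit rates with the app on and off. At 0.70 against 0.85 with equal true totals, and the same off/on rate ratio in both arms, it is closer to 1 when that ratio is above 0.44 (r = 0), between 0.63 and 2.0 (r = 0.5), or between 0.78 and 1.33 (r = 0.75). If Group 1 alone visits twice as often when off, the offset gives 1/(0.70 + 0.30×2) = 0.77. No offset gives 0.63 at r = 0, 0.83 at r = 0.5 and 0.92 at r = 0.75.

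**Conclusion.** The point holds as a gap in the visit model. Recorded visits are true visits times capture; capture depends on the app being on; and the model has no term for it. A between-arm capture ratio that changes over the month biases the planned trajectory comparison, in either direction. A constant ratio biases only the group term. Equal capture or equal decline leaves the between-arm comparison intact.

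The sizes shown are illustrations. They rest on assumed uptimes, an assumed share of hand registration, weekly periods and equal allocation. They show that a moderate drift in one arm would matter, not that it will occur.

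Severity is minor to moderate. This is a one-month pilot, the analysis sits under a feasibility heading and no decision threshold depends on it. What is at risk is the effect estimate carried into the larger proposal.

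**What to change.** Derive location-logging uptime per participant and period from app or server records. In the visit model, count automatically detected visits within logged uptime, use log(uptime) as offset, and treat periods with no uptime as missing, not zero. State the period length. Report uptime, hand registrations and any changes to detection criteria by arm and period.

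Sensitivity analyses: (a) add hand registrations made during uptime, keeping the offset; (b) all recorded visits without the offset, as now planned. Report any disagreement between the main analysis and (b), because the offset assumes similar visit rates with the app on and off in each arm.

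If uptime cannot be derived, say so, state how app-off periods were handled, report the visit comparison as not adjusted for monitored time, and do not read it as a prompt effect.

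The analysis cost is small: one derived variable and one offset. The open cost is the data. No section says that location timestamps are stored, so this must be confirmed. B.1 says the software runs without an internet connection, so server contact alone would understate uptime. Visits registered while logging was off leave the main count and appear only in (b).
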